[figure not shown]
TREATMENT OF PERI-IMPLANT MUCOSITIS USING AN ER: YAG LASER OR AN ULTRASONIC DEVICE. A RANDOMIZED CLINICAL TRIAL.

Statistical analysis plan NCT 05772299

Statistical analysis plan in the study. "Treatment of periimplant mucositis using an Er: Yag laser or an ultrasonic device. A randomized clinical trial."

The power analysis was based on: If bleeding on probing (BOP) is reduced with $30\% \pm 10$ in the test group and with a $30\% \pm 10$ decrease in the control group, detected at alpha= 0.05 and a power of beta= 0.2. The power analysis showed a minimum of 38 individuals to reach a significant difference. It will be foreseen to incorporate 45 individuals if some of the individuals will not fulfil the study.

The IBM SPSS version 28.0 statistical software package (SPSS Inc., Armonk, NY, USA) for personal computer will be used in the statistical analyses.

Statistics will be calculated as means and standard deviation (SD). To compare inter and intra group differences independent t-test (equal variance not assumed), paired t-test and one-way ANOVA test will be used.

For categorical variables non-parametric chi-square test will be used. Statistical significance will be set with 80% and at p< 0.05.

Non visits will be recorded as missing data in the statistics.

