- 4. Local Plaque Score. Presence of dental plaque along the mucosal margin at 6 sites of each treated implant recorded after use of disclosing dye and expressed as a percentage of implant sites within each patient.
- 5. Probing pocket depths (PPD) at the implant (6 sites/implant). Recorded at 6 sites of each treated implant to the nearest mm using a plastic probe.
- Recession of the mucosal margin relative to the restoration margin (REC) at the implant buccally. Position of the mucosal margin apical to the restoration margin is positive recession (+), position of the mucosal margin coronal to the restoration margin is negative recession (-).
- Bleeding on probing (BOP) graded 0-3 at the implant (6 sites/implant). Bleeding appearing after measurement of probing depth and expressed as: 0=no bleeding, 1=a dot of bleeding, 2=a line of bleeding, 3=a drop of bleeding
- 8. Presence /absence suppuration (SUP) at the implant (6 sites/implant).
- 9. Presence/absence of bleeding on probing (BOP) at all teeth/implants (4 sites)
- 10. Treatment times
- 11. Patient evaluation of the treatment: Visual analog scale for pain during treatment, the same day after treatment, one day after treatment and three days after treatment. Visual analog scale for aesthetic/satisfaction before the baseline examination and before the examination at 6 months. Postoperativ complications

is asked for in the examination protocol as an open question. Oral health impact profile is measured with the OHIP-14 version.

- All probing measurements will be made using a manual plastic probe.
- Clinical indices concerning probing pocket depths (PPD), bleeding on probing (BOP), plaque and suppuration will be recorded as 6 sites per implant: mesiobuccal, mid-buccal, disto-buccal, disto-lingual, mid-lingual, mesio-lingual.
- Full mouth plaque scores (FMPS) will be recorded as the percentage of total surfaces (4 aspects per tooth/implant) that revealed the presence of plaque (O'Leary et al. 1972). Full mouth bleeding scores (FMBS) will be recorded as the percentage of total surfaces (4 aspects per tooth/implant) that revealed the presence of bleeding.

Statistical power analysis

If BOP is reduced to 30 % \pm 10 in Group A and with 30 % decrease in group B is to be detected at α = 0.05 and a power of β = 0.2, the appropriate number of subjects would be around n = 38. Hence, it is foreseen to incorporate 45 subjects in the study if some of the individuals will not fulfil the study.

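### The sample size of 38 does not follow from its stated inputs: the SAP assumes the same BOP reduction in both arms, so no between-group difference lies behind the claimed 80% power

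*SAP*

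**What the plan says.** The SAP's power paragraph supposes that BOP is "reduced with $30\% \pm 10$ in the test group" and "with a $30\% \pm 10$ decrease in the control group", with alpha 0.05 and beta 0.2. It concludes: "The power analysis showed a minimum of 38 individuals to reach a significant difference". Enrolment is set at 45 to allow for patients who do not complete.

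The protocol, under Statistical power analysis, gives the same 38 and 45 from a different sentence. There, BOP falls *to* 30% ± 10 "in Group A and with 30 % decrease in group B is to be detected", and "the appropriate number of subjects would be around n = 38". It attaches no ± to Group B and gives no baseline BOP.

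On the measure itself, the protocol's Measurements section has two candidates. One is local: "Bleeding on probing (BOP) graded 0-3 at the implant (6 sites/implant"). The other is full-mouth: "Full mouth bleeding scores (FMBS) will be recorded as the percentage of total surfaces". The power paragraphs do not say which of these the 30% refers to.

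**The concern.** A sample size for a test of difference needs a target difference and a standard deviation. The SAP gives the two arms the same mean reduction, so its target difference is zero, yet it reports a finite number that would show a significant difference. The protocol does not supply what is missing: a fall *to* a level in one arm and a fall *by* an amount in the other can be compared only if the starting level is known.

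This is the trial's only sample-size justification. As written, a reader cannot tell what difference in BOP the trial was sized to detect, on which measure, or with what variability. The 80% power cannot be checked, and a non-significant result cannot be judged against a planned effect. With equal reductions written into the plan, p > 0.05 could also be misread as confirming that the devices are equal.

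**Working it through.** **Inputs from the documents.** Reduction 30% ± 10 in each arm (SAP); alpha 0.05 and beta 0.2, so power 80% (both documents); comparison by independent t-test with unequal variances (SAP); total 38, enrolment 45 (both).

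**Inputs that have to be assumed.** ±10 is the SD of the change in BOP percentage; testing is two-sided; allocation is 1:1; 38 is the total. The documents state none of these.

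**1. Try to reproduce 38 from the SAP.** In the normal approximation, n per arm = 2 × SD² × (1.960 + 0.842)² / difference². With SD = 10 and difference = 30 − 30 = 0, the denominator is zero and n is undefined. Treating the figures as proportions, 0.30 against 0.30, fails in the same way. At a true difference of zero, a two-sided 5% test rejects 5% of the time at any sample size.

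**2. Try natural alternative readings** (SD 10 for means, 80% power).

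| Reading | Total N |
|---|---|
| 10-point difference, two-sided 0.05 | 32 (normal), 34 (t-test) |
| Non-inferiority, 10-point margin | 32 (one-sided 0.025), 26 (one-sided 0.05) |
| Equivalence by two one-sided tests, 10-point margin, 0.05 per side | 36 |
| Proportions 0.30 vs 0.70, no continuity correction | 38 (one-sided), 48 (two-sided) |

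Only the one-sided comparison of proportions gives 38. It needs a second proportion that the documents do not state, ignores the ±10, and does not match the planned t-test on means. The SAP speaks of a significant difference, and neither document states a margin.

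**3. Try the protocol's wording.** Let b be baseline BOP in percent. The reduction in A is b − 30. The reduction in B is either 30 points or 0.3 × b. A positive difference means that A falls further. The table uses the t-test with SD 10 in both arms, although the protocol attaches ±10 only to Group A.

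| Baseline b (assumed) | Difference, B falls 30 points | Total N | Difference, B falls 30% relative | Total N |
|---|---|---|---|---|
| 50% | −10 | 34 | 5 | 128 |
| 55% | −5 | 128 | 8.5 | 46 |
| 60% | 0 | none | 12 | 24 |

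N depends heavily on a baseline that is not given. A total of 38 does arise at particular baselines: about 56.4% on the relative reading (0.7 × 56.4 − 30 = 9.48 points), or about 50.5% or 69.5% on the 30-point reading (a difference of 9.5 points either way, favouring the control at 50.5%). No such baseline is stated.

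**4. Back-calculate what 38 can detect.** Two-sample t-test, noncentral t, 19 per arm, two-sided 0.05.

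| True difference (SD 10) | Power |
|---|---|
| 0 points | 5% |
| 3 points | 14.7% |
| 5 points | 32.3% |
| 9.4 points | 80.5% |
| 10 points | 85.1% |

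A simulation of the unequal-variance t-test (200,000 runs) agrees: 5.0% at 0, 32.3% at 5, 80.6% at 9.4 and 84.9% at 10 points.

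The difference for 80% power at 19 per arm is 9.34 points at SD 10. The normal approximation gives 10 × √(2/19) × 2.802 = 9.09. The result scales with the SD: 7.47 points at SD 8, 11.21 at SD 12 and 14.01 at SD 15. If all 45 are evaluable (22 and 23), it is 8.55 points at SD 10.

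**5. Expected precision.** The half-width of the 95% CI at 19 per arm and SD 10 is 2.028 × 10 × √(2/19) = 6.58 points.

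**The case against.** The best case for the plan is that the protocol is incomplete rather than wrong. A fall to 30% in one arm and a 30% fall in the other do differ at most baselines, and at baselines near 50.5%, 56.4% or 69.5% the protocol's sentence gives 38. The SAP's wording may then be a copying slip for the protocol's. This is plausible and cannot be excluded, and it is why the finding against the protocol is limited to a missing input. But the baseline is not stated, and the SAP sentence still contradicts itself.

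A second point is that the 5% rejection rate at zero difference is simply alpha. It describes the sentence, not the trial's real power. That is correct: the defect is that the figure cannot be reproduced, and nothing here shows that 38 is too small.

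A third point is that any replacement sentence rests on SD 10 and equal arms, which the documents do not establish. If the measure were the percentage of bleeding sites on a single implant, six sites would move it in steps of 16.7 points (100/6), and nothing in the documents supports SD 10 for it. That also stands. The replacement text should therefore state its assumptions and carry the SD range.

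**Conclusion.** The concern holds, with high confidence, and must be fixed. The SAP's inputs imply a zero difference, so neither 38 nor 80% power follows from them. The protocol's version cannot be evaluated without a baseline BOP, and most of the natural alternative readings miss 38. Every route that does reach 38 brings in an input that neither document states.

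If ±10 is the SD of the change in BOP percentage, with 1:1 allocation and two-sided testing, the chosen size has 80% power for about 9.3 points (7.5 to 14.0 points for SDs of 8 to 15) and about 32% for 5 points at SD 10. That describes what the size can do. It is solved from 38, so it is not evidence that 38 was adequate or that 9.3 points was the intended target.

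**What to change.** Keep 45 patients and the planned test. Then:

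- Reconcile the SAP's power paragraph with the protocol's Statistical power analysis section, and remove the equal-reduction wording.
- Name the BOP measure the percentage refers to. Say whether ±10 is an SD and of what. State sidedness, allocation ratio and that 38 is the total, if it is.
- If the sponsor holds the original between-group difference and SD, give them in both documents and recompute the power. If equivalence or non-inferiority was intended, say so and state the margin.
- Otherwise, state what the size can detect, for example: *Back-calculated, not the original design basis: assuming that ±10 is the SD of the change in BOP percentage and that allocation is 1:1, 38 evaluable patients (19 per arm) give 80% power at two-sided alpha 0.05 to detect a between-group difference of about 9.4 percentage points (85% for 10 points, 32% for 5 points). The detectable difference is 7.5 points at SD 8, 11.2 at SD 12 and 14.0 at SD 15.*
- Report the between-group difference with its 95% CI (expected half-width about ±6.6 points at 19 per arm and SD 10), and do not read p > 0.05 as equivalence.

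The cost is wording in two documents, with no extra patients and no change of test. The downside is that the stated capability looks less favourable, and that a back-calculated difference openly admits that the original basis is not on record.

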To assess the clinical outcome over 6 months following treatment with non-surgical debridement using a Er: YAG laser device (AdvErL EVO, Morita corporation, Japan) or with the use mechanical therapy using ultrasonic device with a specially designed tip (EMS, Switzerland)

Materials and methods

Outcome variables

- The extent of gingival inflammation (bleeding on probing BOP)
- Clinical probing pocket depth values
- Clinical registration of suppuration
- Recession of the peri-implant mucosal margin at test and control sites between baseline and at study endpoint (6 months)
- The treatment times
- Changes in "bone levels" (measured from periapical radiographs (see below)
- The prevalence of implant loss

Subject screening

Exclusion criteria

- Subjects with uncontrolled diabetes mellitus (HbA1c > 6.5)
- Subjects requiring prophylactic antibiotics
- Subjects taking prednisolone
- Subjects taking medications known to have effects on gingival growth

• Subjects with a history of taking systemic antibiotics in the preceding 1 month

Inclusion criteria - Presence of peri-implant mucositis

Following a review of the medical history (see exclusion criteria) a full mouth routine periodontal examination, including analysis of available radiographs, will be performed. Subjects who consent and:

- Have a minimum of one or more peri-implant sites with probing depth ≥ 4 mm combined with bleeding and/or pus on probing using 0.2 N probing force.
- 2. No peri-implant marginal bone loss (as determined from a comparison of the bone level one year following implant reconstruction with the bone level at screening (screening radiograph)
- A limited allowed bone loss ≤ 2mm measured from the implant shoulder (as a consequence of remodeling during the healing process)

Intraoral radiographs

Intraoral standardized radiographs of the site of interest will be taken at baseline and at 6 months. Radiographs will be analysed by an independent and blinded examiner.

Treatment procedure

Baseline measurements will be performed, and the patients are randomized into treatment groups A or B. The treatment will be performed by a dentist not involved in the registrations in order to avoid bias. Following treatment, the patients will be instructed in proper homecare using a toothbrush and interproximal aids as needed.

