Group A will be treated using the ER: YAG laser device (AdvErL EVO, Morita Corporation, Japan). The tip is placed in the pocket mesially, lingually, distally and buccally. Careful attempts are to cover the full circumference of the implant. Moving motion would be from bottom to coronal, sweeping motion also covering the soft tissue surface.

Group B will be treated using an ultrasonic device with PEEK coated tips (EMS, Switzerland). The tip is placed in the pocket mesially, lingually, distally and buccally. Careful attempts are to cover the full circumference of the implant.

Material and settings

The device used for the clinical study for Group A will be an Er:YAG laser device (AdvErL EVO, J. MORITA MFG. CORP., Japan) using a below prameter. Group B will receive standard of care using an ultrasonic device with plastic coated tips.

Parameter of Er:YAG laser AdvErL EVO (on the display)

Tip:PS400T Power:30-50mJ Frequency:10PPS Air/Water:7/7

Patient entry

The study will be submitted to the Ethics committee in Uppsala and written consent will be obtained from all subjects to be entered in the study. Once the entry criteria have been confirmed the subject will be entered to the study and assigned a patient number.

After having been entered into the study, subjects will be randomly assigned to one of the two treatment regimens. Random assignment will be performed according to predefined randomisation.

Subject protection – monitoring of adverse events

At each visit the clinician will evaluate patients for any adverse events. Should a patient require any treatment during the course of the study, the necessary treatment will be provided at the discretion of the clinician and according to the current standard of care. All adverse events related to the treatment provided will be recorded. The investigation will be performed according to the principles of the Declaration of Helsinki on experimentation involving human subjects.

Measurements

One and the same examiner, unaware of treatment group for the patient, will perform all the measurements. Before treatment the following baseline measurements will be recorded:

- 1. Intraoral photographs of the implant site
- 2. Presence/absence of hyperplasia
- 3. Full mouth plaque score (FMPS). Presence of dental plaque along the gingival/mucosal margin recorded after use of disclosing dye and expressed as a percentage of examined sites within each patient (4 sites per tooth and implant).

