Allocation concealment

Assignment to test and control group will be made using pre-prepared randomization in groups A or B. Cards with group identification will be prepared and placed in numbered envelopes after randomization. This will be done by a person not involved in the treatment or diagnosis of patients. As a new patient is admitted to the study the treating clinician takes the next numbered envelope then assigning the patient to either group A or B. The code for treatment A and B will be broken once the study is completed and the data set is locked.

Clinical registrations and treatment at baseline

- Clinical photo
- Presence/absence of plaque (6 sites/implant)
- PPD (6 sites/implant)

- Recession of the buccal mucosal margin
- BOP (6 sites/implant) graded
- Presence/absence of suppuration (6 sites/implant)
- FMPS (4 sites per tooth/implant)
- FMBS (4 sites per tooth/implant)
- Prescence/absence of hyperplasia
- Radiograph of the treated site
- Oral hygiene instruction + subgingival treatment in accordance to randomization
- Patient evaluation of the treatment including a VAS scale for pain. And another for aesthetic/satisfaction. OHIP-14 for quality of life assessment in relation to oral health.

Clinical registrations - 1 month

- Clinical photo
- Presence/absence of plaque (6 sites/implant)
- PPD (6 sites/implant)
- BOP (6 sites/implant) graded
- Presence/absence of suppuration (6 sites/implant
- FMPS (4 sites per tooth/implant)
- Re-instructions in oral hygiene procedures

Clinical registrations and supportive treatment at 3 months

- Clinical photo
- Presence/absence of plaque (6 sites/implant)
- PPD (6 sites/implant)
- Recession of the buccal mucosal margin
- BOP (6 sites/implant) graded
- Presence/absence of suppuration (6 sites/implant)

- Presence/absence of hyperplasia
- FMPS (4 sites per tooth/implant)
- FMBS (4 sites per tooth/implant)
- Oral hygiene instruction + subgingival treatment in accordance to randomization
- Patient evaluation of the treatment including a VAS scale for pain.

Clinical registrations and therapy at 6 months

- Clinical photo
- Presence/absence of plaque (6 sites/implant)
- PPD (6 sites/implant)
- Recession of the buccal mucosal margin
- BOP (6 sites/implant) graded
- Presence/absence of suppuration (6 sites/implant)
- Presence/absence of hyperplasia
- FMPS (4 sites per tooth/implant)
- FMBS (4 sites per tooth/implant)
- Radiograph of the treated site.

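### The SAP compares arms without adjusting for baseline and does not say whether the t-test uses 6-month values or changes; ANCOVA on each outcome's own baseline would be a cheap gain in precision.

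*SAP*

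**What the plan says.** The SAP's statistical methods paragraph is the only analysis text in either document. For continuous outcomes it reads: "To compare inter and intra group differences independent t-test (equal variance not assumed), paired t-test and one-way ANOVA test will be used". The only other test named is chi-square for categorical variables. No covariate, ANCOVA or regression model appears, and the protocol has no analysis section that adds one.

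The scale of the between-arm comparison is not stated, and the surrounding wording points both ways:

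- The SAP power paragraph uses change wording: "If bleeding on probing (BOP) is reduced with $30\% \pm 10$ in the test group", with the same figure for the control group.
- The protocol's Statistical power analysis gives Group A's figure as a level reached and Group B's as a decrease.
- The protocol's Outcome variables list words one outcome as a change, "Recession of the peri-implant mucosal margin at test and control sites between baseline and at study endpoint (6 months", and does the same for bone level. Pocket depth is listed only as values.

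Baselines are available. The protocol's Measurements section says "Before treatment the following baseline measurements will be recorded", and its list includes pocket depth, recession and "Bleeding on probing (BOP) graded 0-3 at the implant (6 sites/implant". The same three items appear under "Clinical registrations and therapy at 6 months".

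**The concern.** The paired t-test works within an arm, and one-way ANOVA with two arms is the equal-variance t-test, so neither adds any adjustment. The between-arm result therefore rests on an unadjusted t-test of an unnamed quantity.

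The two possible quantities behave differently. A t-test on 6-month values wastes information when baseline and follow-up are strongly correlated. A t-test on changes adds noise when they are weakly correlated. The plan gives no correlation, so it cannot be said which version it would be better off with.

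A chance baseline difference between arms also moves the two estimates in opposite directions. With the scale unstated, the choice could be made after the data are seen.

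**Working it through.** **1. Inputs.** Alpha and power come from the SAP ("decrease in the control group, detected at alpha= 0.05 and a power of beta= 0.2"; "Statistical significance will be set with 80% and at p< 0.05"). Sidedness is not stated, so two-sided is assumed. The minimum of 38 is taken as a total, because 45 is the planned enrolment, and 1:1 allocation is assumed, giving 19 per arm. The documents do not say what ± 10 is. It is read here as an SD of change, with the other reading in step 5. The baseline to 6-month correlation r is not given, so 0.3, 0.5 and 0.7 are assumed.

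**2. The plan's own figure.** The stated 38 cannot be reproduced. With the same 30% reduction in both arms the difference is 0 and no finite sample size exists. With SD 10 and 19 per arm, 80% power corresponds to a back-solved difference of 10 × (1.960 + 0.842) × √(2/19) = 9.09 points (normal), or 9.34 with the noncentral t. That defect is separate. The variance ratios below need neither an effect size nor an SD.

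**3. Variances**, with equal SDs at both visits and the 6-month t-test set to 1:

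- change t-test: 2(1 − r)
- ANCOVA: (1 − r²) × 35/34, where 35/34 = 1 + 1/(38 − 4) is the expected cost of estimating the slope
- ANCOVA relative to change: (1 + r)/2 × 35/34

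Detectable differences use the noncentral t with 36 df (t-tests) or 35 df (ANCOVA). The SD of a single visit is 10/√(2(1 − r)).

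| | r = 0.3 | r = 0.5 | r = 0.7 |
|---|---|---|---|
| ANCOVA variance / change t-test | 0.669 | 0.772 | 0.875 |
| ANCOVA variance / 6-month t-test | 0.937 | 0.772 | 0.525 |
| SD at one visit | 8.45 | 10.0 | 12.91 |
| Detectable, change t-test | 9.34 | 9.34 | 9.34 |
| Detectable, 6-month t-test | 7.89 | 9.34 | 12.06 |
| Detectable, ANCOVA | 7.65 | 8.21 | 8.74 |

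The better t-test switches at r = 0.5. ANCOVA loses to the 6-month t-test only below r = √(1/35) = 0.169. At r = 0 it detects 6.71 points against 6.61. Against the change t-test, break-even is at r = 2 × 34/35 − 1 = 0.943.

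**4. Chance imbalance.** The baseline difference between arms has standard error SD × √(2/19). The chance that it exceeds 5 points in either direction is 6.8% / 12.3% / 23.3%. Given a 5-point difference, the expected shift is 5r = 1.5 / 2.5 / 3.5 points for the 6-month t-test and −5(1 − r) = −3.5 / −2.5 / −1.5 for the change t-test. ANCOVA removes this shift if the relation is linear.

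**5. If ± 10 is the SD of 6-month values**, power at a difference of 9.34 is 80% for the 6-month t-test, 66% / 80% / 95% for the change t-test and 82% / 89% / 97% for ANCOVA. The ordering is unchanged.

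**6. Simulation** (normal data, SD of change 10, 19 per arm, difference 9.34, 20,000 trials). HC3 is a small-sample robust standard error.

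| r | Welch, 6-month | Welch, change | ANCOVA | ANCOVA with HC3 |
|---|---|---|---|---|
| 0 | 97.6% | 79.6% | 97.2% | 96.5% |
| 0.1 | 96.0% | 80.1% | 95.8% | 94.9% |
| 0.3 | 90.9% | 79.4% | 92.4% | 91.1% |
| 0.5 | 80.5% | 80.2% | 89.3% | 87.4% |
| 0.7 | 58.2% | 79.5% | 84.5% | 82.3% |

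Type I error (10,000 trials) was 4.8–5.3% for Welch and ANCOVA, and 4.0–4.4% with HC3.

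**The case against.** The strongest reply is that omitting ANCOVA is not an error, and that the size of the gain is assumed. Four parts of it deserve an answer.

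- **Scale.** The SAP power paragraph and the bone-level outcome both use change wording. If change is what is meant, the comparison with a 6-month t-test falls away. The protocol's level wording for Group A cuts the other way, so the ambiguity stands.
- **Equal SDs.** Entry is selected on pocket depth with bleeding or pus, and treatment follows, so equal spread is not assured. With k = baseline SD / 6-month SD, the ANCOVA to change ratio is (1 − r²)(35/34)/(1 + k² − 2rk). At r = 0.3 / 0.5 / 0.7 this is 0.99 / 1.03 / 0.95 for k = 0.5, 0.84 / 0.95 / 1.02 for k = 0.75 and 0.40 / 0.44 / 0.46 for k = 1.5. The gain can therefore vanish. The loss stays bounded: ANCOVA estimates the best slope, while the two t-tests fix it at 0 or 1, so the ratio cannot exceed 35/34 = 1.03.
- **Unequal variances.** The SAP chose a test that does not assume equal variances. Like for like, ANCOVA with HC3 is about 1 power point below a Welch test of 6-month values at r = 0 and 0.1, and level with it at r = 0.3. This stands if 6-month values are the intended scale.
- **Discrete data.** For one implant, the percentage of bleeding sites takes only seven values, 16.7 points apart, and the simulation in the working is normal. A further simulation of six-site percentages kept type I error near 5%. ANCOVA power was equal to or above both t-tests, to within 0.5 point at low correlation.

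**Conclusion.** The point holds as an optional improvement. That the plan has no baseline adjustment and does not state the scale of its between-arm test is certain from the text. The planned tests remain valid.

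The size of the gain is illustrative. It rests on an assumed r of 0.3 to 0.7, equal SDs, an SD of 10 and 19 per arm. On those assumptions ANCOVA has 12.5% to 33% less variance than a change t-test and 6% to 47% less than a 6-month t-test. Outside them the gain may be nil, but the expected cost stays near 3% of variance. ANCOVA is thus best or close to best without anyone having to guess r. Even if the sponsor declines it, the scale of the t-test still has to be stated.

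**What to change.** Add a short paragraph to the SAP:

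1. Define the patient-level bleeding summary, for example the percentage of the treated implants' sites that bleed. The model needs this.
2. For each continuous outcome with a baseline value, make the main between-arm analysis an ANCOVA of the patient-level 6-month value on treatment group and that outcome's own baseline, with no other covariate. Report the adjusted mean difference with its 95% confidence interval.
3. Keep the Welch t-test as a sensitivity analysis and state whether it uses the 6-month value or the change.
4. If robust standard errors are wanted, name a small-sample form such as HC3 and accept roughly 1 to 2 points of power.

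Treatment time has no baseline and stays with the Welch test. No new data or visits are needed. The statistical cost is one degree of freedom, about 3% of variance at 38 patients.

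### Adjusting the 6-month comparison for baseline is a cheap gain in precision that the SAP's unadjusted t-test leaves unused

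*SAP*

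**What the plan says.** The SAP has one sentence on continuous outcomes: "To compare inter and intra group differences independent t-test (equal variance not assumed), paired t-test and one-way ANOVA test will be used". It names no outcome, visit, covariate or ANOVA factor, and it does not say whether the between-arm test is on the 6-month value or on change. The protocol has a power paragraph but no analysis section, so nothing elsewhere fills these gaps.

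The baseline data exist. Protocol, Measurements: "Before treatment the following baseline measurements will be recorded". The list that follows includes plaque scores, probing depth (PPD), buccal recession, graded bleeding (BOP) and full-mouth bleeding. Protocol, Intraoral radiographs: "Intraoral standardized radiographs of the site of interest will be taken at baseline and at 6 months". For patient-reported appearance, Measurements gives: "Visual analog scale for aesthetic/satisfaction before the baseline examination and before the examination at 6 months". Clinical registrations follow at 1, 3 and 6 months in the same patients.

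Some wording points to change scores. Outcome variables lists "Recession of the peri-implant mucosal margin at test and control sites between baseline and at study endpoint (6 months" and words bone level as a change, and the SAP's power paragraph describes BOP as a reduction. None of this is carried into the SAP's analysis sentence.

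On size, the SAP gives a minimum of 38 and adds: "It will be foreseen to incorporate 45 individuals if some of the individuals will not fulfil the study".

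**The concern.** In a randomised trial, a baseline value that predicts the 6-month value explains part of the outcome variance. An unadjusted test on 6-month values leaves that part in the error term. A test on change removes some of it but adds the measurement noise of the baseline. Adjusting for baseline does at least as well as either in large samples, and the data are already being collected. With about 38 evaluable patients, precision is scarce.

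Which unadjusted test is the worse choice depends on a correlation that is not known in advance. While the SAP leaves value or change unstated, there are also two candidate p-values for each 6-month comparison.

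The listed one-way ANOVA is a lesser matter. Between two arms it repeats the equal-variance t-test. Across visits it would be unsuitable if the visits were treated as independent groups.

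**Working it through.** **The plan's own figure.** The SAP's inputs (a 30% ± 10 reduction in both arms) give a difference of zero, so no finite sample size follows and 38 cannot be reproduced. If ±10 is an SD, 19 per arm gives 80% power for (1.960 + 0.842) × 10 × √(2/19) = 9.1 points, a difference stated nowhere. That is a separate matter; only the number 38 is used here.

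**Inputs.** From the documents: two arms, 38 evaluable, alpha 0.05, visits at baseline, 1, 3 and 6 months. Assumed, because the documents are silent: 1:1 split (19 per arm), two-sided test, normal data with equal SDs, difference 0.8 SD, correlation ρ = 0.3 / 0.5 / 0.7.

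**Step 1: variance of the 6-month contrast** (unit SD, n per arm, large samples).
- Welch on values: 2/n
- Welch on change: (2/n) × 2(1 − ρ)
- ANCOVA: (2/n) × (1 − ρ²)

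Values over ANCOVA is 1/(1 − ρ²) = 1.10 / 1.33 / 1.96. Change over ANCOVA is 2/(1 + ρ) = 1.54 / 1.33 / 1.18. Estimating the slope costs a factor 1 + 1/(38 − 5) = 1.03. Dividing by it gives 1.07 / 1.29 / 1.90 and 1.49 / 1.29 / 1.14. Simulation (40,000 trials, 19 vs 19) gives 1.07 / 1.31 / 1.91 and 1.50 / 1.29 / 1.14.

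**Step 2: power at 0.8 SD** (same simulations). Normal-approximation check for values: 0.8/√(2/19) − 1.96 = 0.51, or about 69%; the t-test is slightly lower.

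| Analysis | ρ = 0.3 | ρ = 0.5 | ρ = 0.7 |
|---|---|---|---|
| Welch, 6-month value | 67% | 67% | 67% |
| Welch, change | 53% | 67% | 87% |
| ANCOVA, classical SE | 70% | 78% | 91% |
| ANCOVA, HC3 SE | 67% | 75% | 90% |

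The two Welch tests and classical ANCOVA held 4.9–5.0% type I error with equal SDs. Mean 95% CI half-widths, in SD units, were 0.65 / 0.65 / 0.65 (values), 0.77 / 0.65 / 0.51 (change) and 0.63 / 0.58 / 0.47 (classical ANCOVA).

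**Step 3: unequal variances.** Type I error with residual SD ratio 2 and ρ = 0.5 (20,000 trials):

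| Arm sizes | Classical ANCOVA | HC3 |
|---|---|---|
| 19 vs 19 | 5.0% | 4.3% |
| 16 vs 22, larger SD in the smaller arm | 7.9% | 4.8% |
| 22 vs 16, larger SD in the larger arm | 3.3% | 4.1% |

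Two repeat runs of the 16 vs 22 case gave 7.2% and 7.4% for classical ANCOVA, against 4.8% and 4.9% for Welch.

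**Step 4: one-way ANOVA.** Between two arms F = t². In one simulated 19 + 19 sample F was 1.4753, with p = 0.2324 (the same as the pooled t-test) against 0.2354 for Welch. Across four visits in one arm, taken as independent groups, the between-visit mean square has null expectation 1 − ρ while the error mean square has expectation 1, so F is too small. Simulated type I error (n = 19) is 1.3 / 0.3 / <0.1% instead of 5%; the paired t-test between two visits gives 4.9 / 5.0 / 5.1%. Power for a 0.5 SD drop after baseline is 23 / 17 / 11%, against 42 / 56 / 80% for repeated-measures ANOVA.

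**Step 5: would a mixed model add more?** With 7 of 45 patients missing month 6 at random, the variance of ANCOVA in completers is only 0.5 / 1.5 / 3% larger than that of a mixed model over all visits. It is not worth a second analysis.

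**The case against.** The strongest reply is that nothing here is wrong. Randomisation makes the unadjusted Welch test valid on values or on change, and the gain rests on an assumed correlation. Both points stand. Entry criteria that narrow the baseline range could put the correlation at the low end, where the gain over a test on values is about 3 power points.

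The wording for BOP, recession and bone level already leans towards change, which partly uses the baseline. That stands too. For those outcomes the relevant excess variance is the change-score figure (50 / 29 / 14%), not the 91% for values at ρ = 0.7. The SAP still has to say which is meant.

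The SAP chose a test that does not assume equal variances, and classical ANCOVA gives that up. This is a real cost, since no allocation ratio or blocking is stated and 45 is odd. HC3 restores the protection, but at ρ = 0.3 its power (66.8%) only matches Welch on values (67.0%).

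The simulations use normal data. Six-site percentages are coarse and bounded, so BOP may gain less.

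Three stronger readings go beyond the documents:
- A reader might infer that the between-arm result would be biased or prone to false positives. A randomised unadjusted comparison is neither. Pooling visits as independent rows would inflate error, but the SAP does not describe that.
- A reader might infer that the SAP commits to an invalid ANOVA across visits. It names no factor, and a one-way repeated-measures ANOVA is a possible meaning.
- A reader might take "expressed as a percentage of implant sites within each patient" as a definition of patient-level BOP. Those words belong to the Local Plaque Score; implant BOP is graded 0–3 at six sites, with no patient-level summary defined.

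**Conclusion.** The point holds as a cheap improvement in precision, not as an error in the randomised comparison. Under the stated assumptions classical ANCOVA had more power than both unadjusted tests at every correlation tried: by 3 to 24 percentage points over values and by 4 to 17 over change. With HC3 it matched or beat both, with type I error of 4–5% in the settings tried. The size depends on a correlation the documents do not give and on approximate normality.

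The missing choice between value and change is a genuine gap in the SAP, narrower for BOP, recession and bone level than for the other outcomes. The ANOVA issue is minor. It is redundant between arms. Across visits it is a problem only if they are treated as independent groups, and then it is too conservative and affects within-arm change alone.

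**What to change.** In the SAP:

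1. For continuous patient-level outcomes with a value clearly recorded before treatment, make the 6-month between-arm comparison an ANCOVA of the 6-month value on treatment and baseline value, with a 95% CI. This covers mean PPD, plaque scores, recession, full-mouth bleeding score, bone level and aesthetic VAS.
2. Define a patient-level BOP summary first, then analyse it in the same way.
3. Fix one standard error in advance: either HC3 for the main analysis, or the classical one with HC3 as a sensitivity analysis.
4. Include OHIP-14 only if its first administration precedes treatment. The documents do not settle this: Measurements puts it in the same item as pain during and after treatment, and the baseline schedule lists it after the treatment step.
5. Do not use one-way ANOVA between the arms or across visits as independent groups. For within-arm change use the paired t-test already named, or a repeated-measures ANOVA.
6. Leave outside this model "The treatment times" (these arise during the randomised treatment, so the first value must not be a covariate), pain VAS (no pre-treatment value) and binary outcomes.

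The cost is a few sentences and one ANCOVA per outcome in the planned software, with no new data. The downsides are an assumed common baseline slope, loss of unequal-variance protection unless HC3 is used, and little gain if the correlation is low.
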